Recruitment will coincide with the CONTROL Study. Specifically, participants will be screened by the CONTROL Study staff to determine if they meet the study criteria. This includes participants between the ages of 65 – 95 years for the older adult participants and 65 – 85 for the post-stroke participants. The exclusion criteria include participants who have contraindications to non-invasive brain stimulation (i.e., TMS). This would include having metal in the head, a pacemaker, a wound on the scalp, or a history of seizures. Additionally, medications affecting the central nervous system including, but not limited to, benzodiazepines, anti-cholinergic medication and GABAergic medication will be exclusionary as they could influence the results of TMS.

Informed Consent and Onsite Screening Visit

Participants will undergo informed consent for the CONTROL Study and at that time will be invited to undergo an additional informed consent for this study. Prior to the participant signing the additional consent form research staff will explain the TMS study protocol to participants. For participants who wish not to participate in the TMS visit they may continue with the CONTROL Study protocol.

At the discretion of the Principal Investigator, any individual may be deemed ineligible for further participation in this study if there are concerns about the individual's capability to perform study procedures or if it may be unsafe for the volunteer to participate in the study.

Transcranial Magnetic Stimulation (TMS) Visit

Various assessments of muscle strength, neural control, and health and independence will be made during the TMS assessment visit. These assessments include:

Maximal Force Assessment

Participants will perform a series of maximal voluntary contractions (MVCs) to determine the maximal tibialis anterior strength output for each leg. On separate trials, participants will be encouraged to produce as much force during a dorsiflexion as possible with each tibialis

anterior muscle. Once force output for subsequent trials is within 10% the largest force producing trial will be recorded and used during the cSP TMS trials.

Electromyography (EMG)

EMG electrodes will be placed on each tibialis anterior muscle which will be used to measure muscle activity during the TMS trials. Please see the section Transcranial Magnetic Stimulation below for more information.

Transcranial Magnetic Stimulation (TMS)

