Prior to starting TMS, participants will first complete a TMS safety screening questionnaire. The answers to this safety screening will be reviewed and approved by the researcher performing TMS and/or the PI. Like figure 1 but on the tibialis anterior muscles rather than the vastus medialis oblique's participants will have two surface EMG electrodes placed on each muscle belly and one on a bony landmark (e.g., patella).

Participants will be seated in the TMS chair. Then research staff will measure the participants head to locate the center. This is completed by identifying the middle points when measuring from the nasion to inion and from tragus to tragus. Once the center of the head is determined we will measure laterally 1 cm on both cortical hemispheres this point will denote the starting spot for stimulation. After locating the general location, the research staff will work to identify a more precise location for stimulation by incrementally increasing the stimulation intensity and systematically moving the TMS coil around until stimulation results in a consistent muscle response. Once an initial muscle response is observed stimulation intensity will be determined to consistently generate an appropriate muscle response and amplitude. This procedure will be conducted on both cortical hemispheres.

Figure 1: Example of TMS participant set up

Following the determination of location and intensity for stimulation the tibialis anterior muscles, the 6 TMS trials will be performed at random. Each of these trials will be roughly three minutes in length and will include collection of the cortical silent period, short interval intracortical inhibition, and long interval intracortical inhibition for each hemisphere independently.

Questionnaires

We will administer two questionnaires aimed at assessing self-reported measures of health and independence when performing activities of daily living. Both are short, simple, paper-based questionnaires. Specific examples include:

- Short Form-36 – is a set of 36 questions aimed at assessing self-reported measures of health.
- Katz Index of Independence – is a set of questions aimed at assessing one's level of independence when performing activities of daily living.

Possible Discomforts and Risks:

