There is a risk that participants may find the questionnaires uncomfortable or embarrassing if they feel uncomfortable with their answers. In an attempt to alleviate these feelings participants may skip any question that they do not wish to respond to.

Falls. While we do not anticipate a fall occurring there is the potential that a participant could fall while getting into or out of the Biodex seat (Figure 1). To mitigate this risk the Biodex seat rotates and lowers. Additionally, study staff will be present to help participants safely navigate their body position into the seat. Once seated, participants will be securely harnessed in (similar to a seatbelt in a vehicle).

Headache. Although rare, the most common side effect from TMS brain stimulation is headache. However, individuals should not, participate if they have a history of migraine or other types of severe or frequent headaches. It is also possible that participants may experience some neck stiffness or neck pain. This is believed to be due to the straight posture of the head and neck we will require during the experiment.

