TMS is a safe, non-invasive brain stimulation technique that can be used for both diagnostic and therapeutic procedures. The single and paired pulse TMS techniques that will be performed in this study have been used extensively in thousands of research studies and on tens of thousands of subjects in the United States and around the world. Single and paired pulse TMS techniques are considered very safe when accepted guidelines are followed, and no long-term risks have been reported involving the use of single and paired pulse TMS. For most people, the stimulation is not painful, but occasionally slight discomfort or headache can occur. The headaches go away quickly with nonprescription medication. TMS produces a clicking sound when a current is passed through the stimulation coil. During repetitive TMS stimulation this click can result in ringing in the ear and temporary shifts in your ability to determine the pitch and loudness of sounds if no protection is used. Hearing damage is possible, and one subject suffered permanent hearing damage when hearing protection fell out, although this was done using repetitive TMS (rTMS). This study does NOT include rTMS and only single and paired pulse TMS will be employed in this study. Animal and human studies have shown that earplugs or headphones can effectively prevent the risk of hearing disturbance due to TMS. Therefore, participants will be fitted with earplugs during TMS. If individuals find the procedure too uncomfortable, they may discontinue at any time.

TMS can interfere with implanted medical devices and will not be done in people who have pacemakers, implanted pumps, or stimulators, such as cochlear implants or in people who have metal objects inside the eye or skull (dental work such as fillings and similar procedures do not pose a risk and are acceptable). If participants have an implanted device or metal object that is not safe for TMS, they will not be allowed to participate.

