Important medical events that may not result in death, be life-threatening, or require hospitalization may be considered a serious adverse event when the event may jeopardize the patient or subject and/or may require medical or surgical intervention to prevent one of the outcomes listed in the definition above.

An *unexpected adverse event* is any adverse event that is not consistent with the current investigator brochure, protocol, consent form, or is not part of the normal disease progression. In addition, known adverse events may occur more frequently than expected. If so, then this meets the definition of “unexpected” and must be reported to the IRB.

Protection Against Risk

Staff training: All personnel will be thoroughly trained in the study procedures by the Principal Investigator or other appropriate member of the research team and will complete all required trainings concerning human subjects research at the University of Florida.

Health monitoring and medical response: Volunteers at risk of health problems due to recent history of medical conditions (e.g., serious cardiac or pulmonary conditions) will be excluded, as noted above in the inclusion/exclusion criteria. Any adverse events will be recorded and monitored as required by our University of Florida Institutional Review Board. In the event of a medical emergency at the VA Hospital (our study site) we will call the hospital emergency

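### Does the safety plan rely on a cardiac or pulmonary exclusion that the eligibility criteria never state?

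*Combined protocol and SAP*

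**What the plan says.** Participant Screening (Section 6) gives age ranges for the two groups and then the exclusions: "The exclusion criteria include participants who have contraindications to non-invasive brain stimulation (i.e., TMS"). Examples follow: "This would include having metal in the head, a pacemaker, a wound on the scalp, or a history of seizures". Drugs acting on the central nervous system are also excluded. On who applies the criteria, it says "participants will be screened by the CONTROL Study staff to determine if they meet the study criteria". Under Informed Consent and Onsite Screening Visit, the Principal Investigator may rule anyone out over ability to perform the procedures or because "it may be unsafe for the volunteer to participate in the study".

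Other bars stand elsewhere:

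- Possible Discomforts and Risks says that "individuals should not, participate if they have a history of migraine or other types of severe or frequent headaches", and of devices that "TMS can interfere with implanted medical devices and will not be done in people who have pacemakers, implanted pumps, or stimulators".
- The Transcranial Magnetic Stimulation (TMS) subsection requires a safety questionnaire before stimulation: "The answers to this safety screening will be reviewed and approved by the researcher performing TMS and/or the PI".
- Protection Against Risk adds the cardiac and pulmonary statement, "e.g., serious cardiac or pulmonary conditions) will be excluded, as noted above in the inclusion/exclusion criteria", and then resting heart-rate and blood-pressure limits.

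Protection Against Risk also has two emergency instructions. Emergencies at the VA Hospital, which is the study site, go to the hospital emergency line. Angina at rest, loss of consciousness and cardiac arrest go to 911.

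**The concern.** A safety plan that cites an eligibility criterion should be citing one that exists. Here a reader who goes back to Participant Screening finds no cardiac or pulmonary condition apart from a pacemaker, which is there as a TMS contraindication. The same paragraph does not name migraine or severe headache, nor the resting vital-sign limits, which the text calls contraindications to participation without saying when they apply.

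If CONTROL Study staff screened from that paragraph alone, people the safety plan says are excluded might reach the TMS visit, and the bars might be applied unevenly. The participants are 65 or older, and Table 1 rates the TMS measures as greater than minimal risk. Separately, a cardiac arrest at the study site falls under both emergency instructions, and neither is given precedence.

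**Working it through.** No figure in the plan bears on this point and no formula applies. The check is to set each bar against Participant Screening and ask whether following the whole document would apply it.

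| Bar | Where stated | In Participant Screening? | Applied if the whole plan is followed? |
|---|---|---|---|
| Serious cardiac or pulmonary conditions | Protection Against Risk | No, though cited as being there | Yes, that sentence states the exclusion |
| Migraine, severe or frequent headache | Possible Discomforts and Risks | Not by name; fits the open TMS category | Yes |
| Implanted pumps and stimulators | Possible Discomforts and Risks | Not by name; fits the open TMS category | Yes |
| Resting vital-sign limits | Protection Against Risk | No | Yes, at the latest at the visit |

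**Cardiac and pulmonary.** The cross-reference has two parts: a rule (these volunteers are excluded) and a location (the criteria above). The location is wrong. The rule does not depend on it.

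**Headache and devices.** The exclusion paragraph is worded inclusively and its conditions are examples. Implanted pumps and stimulators are TMS contraindications that it covers without naming. The headache bar is the same kind of item: the protocol gives it as a reason not to take part, directly after naming headache as a TMS side effect. Counting one as covered and the other as missing would be inconsistent.

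**Vital signs.** There are five limits: heart rate above 100 or below 50 bpm, systolic pressure above 180 or below 100 mmHg, and diastolic pressure above 100 mmHg. They stand between a sentence on monitoring before, during and after assessment and the rules for ending activity. A visit-day check is the natural reading. They come after the cross-reference and are thresholds, not medical history, so they cannot be its target.

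**Emergency calls.** The three events listed for 911 would also be medical emergencies if they happened on site, so both instructions cover them there. Neither forbids the other call, and both can be made. This is an overlap in emergency response and has no bearing on who is enrolled.

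**Who could slip through.** This study is an optional visit added to CONTROL. Section 6 says it recruits no one itself, and participants consent to CONTROL as well. Whether anyone with serious cardiac or pulmonary disease could reach the TMS visit therefore depends partly on CONTROL's criteria. Those are not in the document, so the number cannot be derived in either direction.

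**The case for a change.** The strongest case for a change is practical. The protocol says that a safeguard is written in a named place, and it is not there. The backstops cannot be shown to fill the space: CONTROL's criteria are not reproduced, the questionnaire's items are not listed, and the discretion clause names no condition. Screeners work best from one list, and scattered bars invite uneven use. Open wording may bring in further TMS contraindications, but it does not make the reference to a cardiac or pulmonary criterion true.

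The broken reference stands, and so does the last point. What does not follow is a gap in protection. The exclusion is in force in the safety plan's own words, whether or not a backstop repeats it. Gathering every bar into one list would be tidier, but it would add no bar that the protocol lacks, and a list imposed on CONTROL screening might touch a separately approved study. The call overlap also stands as a matter of wording: the two statements must be reconciled, and which call applies is for the investigators.

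**Conclusion.** The concern is right about one cross-reference and does not extend to the plan itself. Protection Against Risk and Participant Screening must be reconciled on where the cardiac and pulmonary exclusion is listed. That is a clerical correction. The timing of the vital-sign limits and the order of emergency calls are details of drafting. None of these points alters an aim, an outcome, the sample size or an analysis.

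This rests on two assumptions: that study staff work from the whole protocol and not from the screening paragraph alone, and that the vital-sign limits are applied at the visit, as their context suggests. If CONTROL's criteria were found to admit people whom this safety plan excludes, and screening relied on those criteria alone, the point would deserve another look. Nothing in the document shows that.

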response line, [name] and alert them to a code blue (medical emergency). Subjects will be able to terminate a study session at their request at any time without prejudice. Minimization of risk during neurorehabilitation and assessments will be accomplished by monitoring vital signs, with prescribed criteria for termination of the testing session. Vital signs will be monitored before, during and after assessment. Contraindications for participation will include resting heart rate >100 bpm or <50 bpm, resting systolic blood pressure >180 mmHg or <100 mm Hg or resting diastolic blood pressure >100 mmHg. Indications to terminate physical activity will include subject complaints of shortness of breath, light-headedness, dizziness, confusion, severe headache, dyspnea or onset of angina. If any of these conditions are greater than mild or persist after rest, the patient's primary physician will be called and patient referred for evaluation. If the patient complains of angina at rest, loss of consciousness occurs, or cardiac arrest, emergency medical services through 911 will be called immediately. Portable defibrillators are available.

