Confidentiality: Data will be used only in aggregate and no identifying characteristics of individuals will be published or presented. Confidentiality of data will be maintained by using research identification numbers that uniquely identify each individual. Safeguards will be established to ensure the security and privacy of participants' study records. Appropriate measures will be taken to prevent unauthorized use of study information. Data other than demographic information will not use names as an identifier. The research ID number will be used. The research records will be kept in a locked room in the study site. The files matching participants' names and demographic information with research ID numbers will be kept in a locked file that uses a different key from that of all other files. Only trained and certified study personnel will have access to these files, and they will be asked to sign a document that they agree to maintain the confidentiality of the information. Electronic records will be stored on password protected network server maintained by the university information technology department. In compliance with the Health Insurance Portability and Accountability Act (HIPAA) and the Standards for Privacy of Individually Identifiable Health Information of the Department of Health and Human Services, we access personal health information and medical records only after receiving signed informed consent.

TMS Safety: Our protocol uses stimulation parameters that are considered standard practice for single- and paired- pulse TMS. These parameters have been used safely in thousands of prior research studies. The most common side effect of TMS is a headache. To minimize risks associated with TMS, participants will complete a pre-TMS screening form and will be monitored throughout the stimulation session. Additionally, participants will be asked to report any discomforts. If stimulation is or becomes uncomfortable, the stimulation levels will be decreased to a comfortable level or will be stopped.

Questionnaire administration: Questionnaire data are collected in secure spaces where the interview cannot be overheard. Participants will be informed that they are not required to answer questions that they do not wish to answer.

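### Do the hospital code-blue line and the 911 call give staff conflicting emergency instructions?

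*Combined protocol and SAP*

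**What the plan says.** Both instructions stand in one paragraph, headed Health monitoring and medical response, under Protection Against Risk in the Data and Safety Monitoring Plan.

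- **Hospital line.** "In the event of a medical emergency at the VA Hospital (our study site) we will call the hospital emergency" and the sentence continues "response line, [name] and alert them to a code blue (medical emergency". The trigger is general (any medical emergency) and the place is stated.
- **911.** "If the patient complains of angina at rest, loss of consciousness occurs, or cardiac arrest, emergency medical services through 911 will be called immediately". The trigger is a list of three events and no place is stated.

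Between them lies a milder tier. For symptoms that are more than mild or that outlast a rest, the patient's "primary physician will be called and patient referred for evaluation".

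The VA Hospital is the only study site named. The Confidentiality paragraph also speaks of one site: "The research records will be kept in a locked room in the study site".

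**The concern.** All three events on the 911 list are medical emergencies in the ordinary sense, and the hospital sentence explains a code blue as a medical emergency without exception. With one named site, a cardiac arrest during a study visit falls under both sentences. The text does not say that 911 is meant only for other places, that both calls are wanted, or which comes first. The word for immediate action is attached only to the 911 call.

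The stake would be patient safety. Under Participant Screening, older adults are enrolled from 65 to 95 years and stroke survivors from 65 to 85. Table 1 puts the three TMS measures that this study adds in its higher risk class. If staff hesitated between two routes, help could come later for the events in which time matters most.

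**Working it through.** No arithmetic applies, and the plan states no figure on this point. The check is to set the two sentences side by side.

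| | Hospital line | 911 |
|---|---|---|
| Trigger | Any medical emergency | Angina at rest, loss of consciousness, cardiac arrest |
| Place | VA Hospital, named as the study site | Not stated |
| Action | Call the response line, raise a code blue | Call emergency medical services at once |
| Excludes the other route? | No | No |

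1. **Do the triggers coincide?** Only in part. The hospital line covers every medical emergency and the 911 sentence covers three. The overlap is those three events.

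2. **Is the place the same?** This is an inference. The hospital sentence carries an express location and the 911 sentence carries none. Applying the latter to the hospital rests on no other site being named. The 911 sentence also follows text about neurorehabilitation and about ending physical activity. This study's own visit consists of strength testing, EMG, TMS in a chair and two questionnaires, while Table 1 assigns the turning measures and the locomotor intervention to the parent CONTROL Study. The sentence may have been written with that wider activity in mind. The document neither confirms nor rules this out.

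3. **Can both instructions be followed?** Yes. A contradiction needs two instructions of which obeying one breaks the other. Here neither says that it replaces the other or that it is the only route. What the text leaves open is scope and order.

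4. **What happens if staff follow the text as written?** Under the hospital line alone, 911 alone, or both, emergency help is called at once. No reading of the paragraph leaves one of the three events without a call.

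5. **What else does the plan provide?** All personnel are trained in the study procedures, vital signs are checked throughout the assessment, and portable defibrillators are on hand. None of this states which call comes first, but it limits how much depends on the wording of these two sentences.

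6. **Does anything statistical depend on it?** No. The aims, the sample size statement in section 10, the outcome measures and the adverse event reporting rules read the same whichever route is used.

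The bracketed gap where the response line is identified is a removal of personal data from the public copy and is not counted against the plan.

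**The case for a change.** The best case for a change is that a safety instruction should not depend on inference. The reading that separates the routes by place is plausible, but the document does not state it and names no other place where study procedures occur. Training built on this text would carry the same ambiguity. The participants are old, the events are grave, and one sentence would cure it.

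Part of this stands. The overlap is real, no text resolves it, and a clarifying line would be cheap. The stronger claims do not stand. It is too much to say that nothing separates the routes, because one sentence has a location condition and the other has none. It is too much to say that staff cannot know what to do, because each instruction is clear and the two can be carried out together. That the wording would delay a response is conjecture; nothing in the document supports or measures such a delay.

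The risk argument also needs trimming. Table 1 puts five of its nine rows in the higher class, and two of those five belong to the CONTROL Study, which leaves 5 − 2 = 3, the TMS measures. The maximal strength test, the main exertion in this study's visit, is in the minimal class.

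**Conclusion.** The concern does not call for a change. For three events at the one named site, the plan gives two emergency instructions without saying how they relate. They overlap and do not exclude each other, and every reading leads to an immediate call for help. The missing detail is whether one or both calls are meant, and in what order. That is for the sponsor and the site to reconcile, and this review takes no view on which route is right.

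The size of the matter is one unstated scope condition, with no effect on the design, the estimates or any conclusion of this pilot. How often the three events might occur cannot be derived from the document.

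The conclusion rests on two assumptions. The first is that the two calls are compatible in practice, which the wording allows. The second is that a team working inside a hospital settles with that hospital how its emergency line and 911 are used. The document does not state this, but it is ordinary local practice. If the site's own rules made the two calls mutually exclusive, the sentences would be in real conflict; nothing in the document suggests that.
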